6.8 Plan to Minimize Loss-to-Follow-up

[figure not shown]
The sample size of up to 300 subjects for this study (minimum of 250) is based on the assumption that over the course of 5 years there will be at least 20% attrition due to Loss-to-Follow-up. All subjects will be offered reimbursement for completing each planned visit. Note that the amount of reimbursement is limited by each Institutional Review Board (IRB).

As part of the informed consent, patients will be asked to agree to follow-up evaluations out to 5 years after Alair treatment. Each subject will be asked to provide an Emergency contact and contact information for mother (if alive) and a nearest living family member who could be used as alternatives to reach the subject. In addition, subject's will be informed that in the event they fail to respond to written communication in the form of letters by recorded delivery, the Site with support from the Sponsor (Asthmatx, Inc.) will enlist the help of a search agency to confirm the subject's contact information.

Sites will be asked to remind subjects that being the first device based procedure for treating asthma, the commitment of the subjects to their participation for the full 5 years is important in understanding all aspects of the Alair treatment.

Figure 3 outlines the steps that will be taken to contact any subject who misses the planned annual follow-up visit so as to ensure adequate follow-up.

Figure 3: Steps to Contact Subjects for Annual Follow-up Visits

In the event that a letter is returned as undeliverable, Asthmatx will enlist the aid of a search agency to confirm the subject's contact information. If existing contact is valid, one more attempt will be made with certified mail within 30 days before the subject is considered as "unable to contact". If new contact information is obtained, contact will be attempted via 2 recorded delivery mails before the subject is considered as "unable to contact". In the event that a subject is Lost-to-Follow-up, their status at the last contact will be reported.

If needed, the Sponsor will offer to cover travel and housing costs for a subject who has relocated to a new city in order for them to return to the clinical study site to complete their annual follow-up evaluations. Alternatively subjects will be allowed to continue follow-up at the closest study site to their new location.

In the event that the subject is unable to complete the annual evaluation during the normal work week (Monday to Friday) because of a change in his/her personal situation, the

Sponsor will work with the site to schedule the evaluation during the weekend days (Saturday or Sunday) provided the subject is agreeable.

Reasons for subject initiated withdrawal from the study will be reported.

An Investigator may withdraw a subject from the study at any time for one or more of the following reasons:

- Subject does not follow instructions given by the Investigator;
- Subject could be harmed by continued participation in the study;
- Subject requires treatment not allowed in the study;
- Subject develops significant other illness such as lung cancer, tuberculosis, emphysema, or heart disease that would compound study validity;
- Subject develops a terminal illness unrelated to their asthma.

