4.0 Objectives with Study Hypotheses

The objective of this study is to evaluate durability of treatment effect and to continue to evaluate the short-term and longer-term safety profile of the Alair System in the United States and Canada in the intended use population (patients 18 years and older with severe persistent asthma) following FDA approval.

Durability of the treatment effect will be evaluated by comparing the proportion of subjects who experience severe exacerbations* during the first year after Alair treatment with the proportion of subjects who experience severe exacerbations during subsequent 12-month periods out to 5 years. Favorable upper 95% confidence limits of the difference in proportion of subjects experiencing severe exacerbations between the subsequent years and the first year will be used to infer a durable treatment effect.

Study Hypothesis: An empirical demonstration of the durability of the treatment effect will be used to show that the proportion of subjects experiencing severe exacerbations in subsequent years compared with the proportion of subjects experiencing severe exacerbations in the first year do not get substantially worse. The primary statistical objective is to demonstrate that the proportion of subjects who experience severe exacerbations in the subsequent 12-month follow-up (for Year 2, Year 3, Year 4 and Year 5 [in 12-month periods]) is not statistically worse when compared with the proportion of the first 12-months, which begins 6-weeks after the last Alair treatment. This objective will be met if the upper 95% confidence limit of the difference in proportions (i.e., the subsequent 12-month proportion minus the first 12-month proportion) is less than 20%. The formal expression of the hypothesis is as follows:

Let π_s and π_f be the 12-month probabilities for the period subsequent to the first period and for the first period, respectively. The primary effectiveness endpoint will be demonstrated by rejecting the null hypothesis $H_0: \pi_s \geq \pi_f + \delta$ in favor of $H_1: \pi_s < \pi_f + \delta$ at an alpha of 0.05, using a δ of 0.20 (i.e., 20%).

The test of hypotheses and/or computation of equivalent confidence limits will be based on large-sample confidence interval estimation methods for independent samples.

* Severe exacerbation defined as worsening of asthma symptoms requiring use of systemic corticosteroids (tablets, suspension, or injection) (NAEPP Guidelines, 2007).

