7.3.5 Bronchial Thermoplasty Treatment

Bronchial thermoplasty with the Alair System will be performed in three bronchoscopy sessions, separated by at least 3 weeks. The areas targeted for treatment with the Alair System are the airways distal to the main stem bronchi (beginning at the lobar bronchi, 2nd Weibel generation) down to airways of 3mm in diameter (about the 6th Weibel generation).

- During the first bronchoscopy session, the right lower lobe (RLL) will be treated.
- During the second bronchoscopy session, the left lower lobe (LLL) will be treated.
- During the third bronchoscopy session, both the right upper lobe (RUL) and the left upper lobe (LUL) will be treated.
- The right middle lobe (RML) will not be treated (see Section 7.3.7).

After the first bronchoscopy session and at all subsequent bronchoscopy sessions, carefully conduct a visual bronchoscopic examination of previously treated airways and document any findings. If any clinically significant findings are observed, subsequent bronchoscopy session should be postponed for at least two weeks and until the subject is clinically stable. At the subsequent bronchoscopy the previously abnormal area should be re-inspected. Complete resolution of any findings must be confirmed and documented in the subject's medical records before subsequent Alair treatments commence. If the abnormal findings persist, Investigator should consult with Sponsor to determine whether to proceed with

further treatments or abandon further treatments. In the event that further treatments are not performed, the subject should remain in the study for continued follow-up.

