7.3.6 Pre-Procedure Evaluations

- Determine if subject has recently had, or is currently experiencing cold or respiratory symptoms.

If subject has recently had or is currently experiencing cold or respiratory symptoms, the treatment session must be rescheduled until the subject no longer has these symptoms. Inform subject that the chance of post-procedure side effects increases under these circumstances.

- Verify that the subject has taken the prescribed 50mg oral prednisone or equivalent per day, for the three days prior to, and on the day of treatment session (prophylactic indication).

If the prescribed prednisone or equivalent was not taken on the three days prior to bronchoscopy, the treatment should be postponed. If the dose of prednisone or equivalent was not taken for the day of the treatment session, an equivalent dose may be given intravenously during the procedure or just after the procedure and prior to release.

- Perform a pregnancy test for female subjects of child bearing potential
 - A positive pregnancy test before the first bronchoscopy session will disqualify the subject from the study.
 - A positive pregnancy test prior to the second bronchoscopy session will result in termination of further bronchoscopy procedures for the subject. However, the subject must be evaluated as per protocol at all planned evaluation visits.
- Perform a post-bronchodilator FEV₁

Postpone treatment session if any of the following conditions apply:

- a. Prescribed prednisone or equivalent was not taken on the three days prior to treatment.
- b. SpO₂ less than 90% on room air in last 48 hours.
- c. Increase in asthma symptoms in last 48 hours requiring more than 4 puffs/day of rescue bronchodilator over normal usage.
- d. Subject is less than 2 weeks from completion of a course of oral corticosteroid use for an exacerbation of asthma.
- e. Subject's post-bronchodilator FEV₁ is less than 85% of baseline/enrollment level.
- f. Subject has an active respiratory infection, active allergic sinusitis, or other clinical instability.
- g. Investigator feels for any reason the treatment should be postponed.
- h. The absence of a companion or caretaker at home to assist on the day of treatment.

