- Activate the RF Controller by pressing the footswitch and deliver RF energy to the target site.
- Collapse the electrode array and reposition the electrode array 5 mm proximally from the previous location. Repeat the delivery of RF energy.
- Continue with treating the length of the airway with contiguous placements and activations of the electrode array.

NOTE: It is expected that each subject will undergo three treatment sessions. If during the first treatment a subject's airways are noted to be unusually small, tortuous, or of such atypical anatomy that either a safe or a complete procedure cannot be performed, do not proceed with treatment; the subject should be withdrawn from the study.

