5. **Other risks:** The possible short-term risk of the Alair treatment may include acute respiratory failure. The theoretical potential long-term risks may include bronchial stenosis, bronchiectasis, and persistent retained secretions, although these events have not been observed in any subject treated to date, including 16 subjects who are beyond two years post-treatment. There may be additional risks that are unknown at this time that may potentially occur as a result of the Alair treatment of asthma patients.

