		10035664	Pneumonia
		10035728	Pneumonia pneumococcal
		10035730	Pneumonia primary atypical
		10062352	Respiratory tract infection
		10060693	Respiratory tract infection bacterial
		10039083	Rhinitis
		10040753	Sinusitis
		10060841	Sinusitis bacterial
		10044008	Tonsillitis
		10046306	Upper respiratory tract infection
		10047473	Viral pharyngitis
		10051513	Viral sinusitis
		10047482	Viral upper respiratory tract infection
10022117	Injury, poisoning and procedural complications	10009913	Collapse of lung
		10069363	Traumatic lung injury
10028395	Musculoskeletal and connective tissue disorders	10050819	Musculoskeletal chest pain
10029104	Neoplasms benign, malignant and unspecified (incl cysts and polyps)	10062042	Lung neoplasm
10029205	Nervous system disorders	10034018	Parosmia
		10040744	Sinus headache

In addition to the complete tabulation of adverse events for all subjects enrolled in the study, adverse events will also be tabulated separately for the subsets of subjects enrolled in sites in the United States and the sites in Canada.

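### Section 6.8 lets an investigator end follow-up because a subject develops a new illness, so later safety events in that outcome-selected group are no longer sought

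*Protocol*

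**What the plan says.** Protocol section 4.0 sets out to "continue to evaluate the short-term and longer-term safety profile of the Alair System". Section 6.8, which is about limiting loss to follow-up, then says "An Investigator may withdraw a subject from the study at any time for one or more of the following reasons" and lists five. The one at issue is "Subject develops significant other illness such as lung cancer, tuberculosis, emphysema, or heart disease that would compound study validity". The others are not following instructions, possible harm from continuing, need for a treatment the study does not allow, and a terminal illness unrelated to asthma. The section does not say whether safety contact continues after such a withdrawal.

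Three passages deal with subjects whose treatment is incomplete:

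- The NOTE in 7.3.7 covers airway anatomy that, in the first session, rules out a safe or complete procedure: "do not proceed with treatment; the subject should be withdrawn from the study".
- Section 7.3.5 covers treatments abandoned after persisting abnormal findings: "In the event that further treatments are not performed, the subject should remain in the study for continued follow-up".
- Section 7.3.6 covers a positive pregnancy test before the second session, which ends further procedures: "However, the subject must be evaluated as per protocol at all planned evaluation visits".

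Protocol section 8.0 has every adverse event monitored until it resolves or stabilizes. SAP 3.1 keeps anyone with at least one procedure in the ITT set.

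**The concern.** The treatment is given in three sessions and is then finished. A subject who develops lung disease in year 3 has no study treatment left to stop, so withdrawal at that point ends only observation.

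The trigger is a health outcome arising after treatment. Protocol section 5.5 excludes emphysema, cancer and clinically significant cardiovascular disease at entry, so a case on study will normally be new. If such subjects leave, the respiratory event, serious event and hospitalization figures for later years come from a cohort from which some of the less healthy members have been removed. The bias would run towards a safer-looking device. The SAP itself treats one of these illnesses as relevant: Table 3 in section 4.6 moves "Lung neoplasm" into the respiratory class so that respiratory events are reported conservatively.

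The early-session question is smaller. A subject bronchoscoped in an incomplete first session might leave before the scheduled post-procedure contacts.

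**Working it through.** **Step 1. What withdrawal ends.** Protocol 6.7 and 7.3.12 to 7.3.13 give the contacts after the 6-week visit: quarterly calls and annual visits with examination and spirometry. New adverse events, emergency visits and hospitalizations are found by asking at these contacts. Section 8.0 continues monitoring of an event already reported, but it does not look for the next one. The loss is therefore later new events and later person-time, not the triggering event.

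**Step 2. Whether the analysis repairs it.**

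- Protocol 6.3 excludes lost subjects from the primary analysis and plans matched-pair sensitivity analyses, two of them with multiple imputation. All concern the primary endpoint.
- SAP 2.1.3 and 6.3 add a tipping-point analysis, also for the primary endpoint only.
- ITT membership keeps the subject in the set but supplies no data after exit.
- SAP 4.6 leaves subjects without a post-treatment visit out of post-treatment summaries.

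Nothing addresses missing later safety events.

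**Step 3. Size.** The plan's own enrolment figure reproduces: 200 / (1 − 0.20) = 250. Table 1's power figures also reproduce to within 2 percentage points and are not affected by this point.

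- Planned follow-up at minimum enrolment, falling evenly from 250 to 200: (250 + 200)/2 × 5 = 225 × 5 = 1,125 subject-years.
- Rate of a listed illness: the documents give none. Assume 0.5% to 2% of subjects a year.
- Cases: 1,125 × 0.005 = 5.6; 1,125 × 0.02 = 22.5.
- Follow-up lost per case, if every case is withdrawn and onset is spread evenly over 5 years: 2.5 years.
- Subject-years lost: 5.6 × 2.5 ≈ 14; 22.5 × 2.5 ≈ 56.
- Share: 14/1,125 ≈ 1%; 56/1,125 = 5%. With these assumptions the share does not depend on enrolment.

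The share of person-time understates the effect if withdrawn subjects have more later events. As an illustration only, take 250 treated, a 2% later serious-event risk in retained subjects, and 20% or 50% in those withdrawn:

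| Withdrawn | True risk at 20% | True risk at 50% | Seen in retained |
|---|---|---|---|
| 3 | (247×0.02 + 3×0.20)/250 = 2.2% | 2.6% | 2.0% |
| 10 | (240×0.02 + 10×0.20)/250 = 2.7% | 3.9% | 2.0% |
| 15 | (235×0.02 + 15×0.20)/250 = 3.1% | 4.9% | 2.0% |

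This shows direction, not expected size, because every risk in it is assumed.

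**Step 4. The first-session NOTE.** The wording of 7.3.5 is general: treatment stops and the subject stays. Its context is findings after an earlier session. The NOTE in 7.3.7 also covers treatment that stops, and there the subject leaves. The NOTE is limited to anatomy, and the six general grounds for ending a bronchoscopy in the same section carry no withdrawal. A subject found unsuitable part-way has had bronchoscopy and sedation. The NOTE does not say whether withdrawal takes effect before the calls on Days 1, 2 and 7 (7.3.9) or the 2-week and 6-week visits (7.3.10, 7.3.11). It is also unclear whether a partly treated subject counts as having been given a procedure for the ITT set.

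**The case against.** The strongest reply is that little is lost:

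- Withdrawal under 6.8 is discretionary and restricted to illness thought to affect study validity.
- The triggering event is recorded, followed and tabulated, and protocol section 15.0 requires interim reports to explain physician-initiated discontinuations and deaths.
- Entry is limited to ages 18 to 65 with under 10 pack-years, so such illness may be uncommon.
- Even the upper figure of 5% of subject-years sits inside the planned 20% attrition.
- For the primary endpoint, the SAP's Complete/Partial set keeps any subject with an exacerbation in the period, whatever the amount of follow-up.

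All of this stands, and it limits the point. It does not remove it, because none of these provisions finds a new event after exit.

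A reader might infer more than the documents support:

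- *That the study stops observing the very subjects who carry its safety signal.* The first event is kept, and nothing in the documents links the listed illnesses to the device. The risks named in 9.1 are different: "The theoretical potential long-term risks may include bronchial stenosis, bronchiectasis, and persistent retained secretions". The list in 6.8 is open-ended, so these could be brought under it, but that is a possibility only.
- *That any aborted first session forces withdrawal.* The NOTE says *should*, not *must*, and covers anatomy only.
- *That 7.3.6 directly contradicts the NOTE.* It concerns subjects who have already had a session, and it disqualifies a subject who tests positive before the first.
- *That losing two or three late events would change the safety conclusion.* With 0 of 200 the one-sided 95% upper limit is 1 − 0.05^(1/200) = 1.5%, but SAP 2.2.1 sets no hypothesis for the secondary (safety) endpoints, and no threshold exists to be crossed.

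**Conclusion.** The point holds as a gap in safety follow-up. As written, section 6.8 allows observation to end because of a post-treatment health outcome, in a study with a longer-term safety objective and no treatment left to stop. Later events and person-time are then lost in a way that depends on outcome, with no planned analysis for the safety endpoints.

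The size is unknown. The figure of at most about 14 to 56 of 1,125 subject-years (1% to 5%) rests on an assumed 0.5% to 2% a year, withdrawal of every case, and 2.5 years lost per case. Actual use of a discretionary rule could be well below that. That the loss falls on less healthy subjects is an inference from the listed reasons, not something the documents measure. Sample size and power are unaffected.

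The 7.3.7 NOTE and 7.3.5 are in tension and must be reconciled. This is a cheap improvement, not a flaw that undermines the study.

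**What to change.** - In 6.8, state that for a subject who has had a study bronchoscopy, developing a new illness is not by itself a reason to end safety follow-up. The existing quarterly calls and annual visits, or calls alone, continue unless the subject declines or continued participation could harm the subject. When treatment sessions stop is a separate matter for the sponsor and is not touched here.
- Flag these subjects in the database and repeat the primary comparison without them as a sensitivity analysis. This answers the worry about validity without discarding safety data.
- Reconcile the 7.3.7 NOTE with 7.3.5 and 7.3.6, stating whether a subject bronchoscoped in an incomplete first session keeps the existing post-procedure adverse-event contacts, and whether that subject belongs to the ITT set.

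The cost is protocol wording, one flag variable, one extra analysis and a few more contacts on the existing schedule. Protocol 6.8 already asks subjects at consent to agree to five years of follow-up. The downside is small: some retained subjects will have exacerbations that are harder to attribute to asthma, which the sensitivity analysis would show.

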7.0 Study Plan

7.1 Test Device

The device being evaluated in this clinical study is the Alair® Bronchial Thermoplasty System (Alair System) (Asthmatx, Inc., Sunnyvale, CA), that consists of the Alair Catheter and the Alair RF Controller.

7.2 Investigator Training

Investigators will be fully trained in the proper use and operation of the Alair System before initiation of any treatments.

- Training will include didactic sessions and hands-on use of the Alair System (using an appropriate anatomical model).
- In addition, on-site training will be provided to the Investigator, Co-Investigators and other study support personnel before the first treatment at each clinical site.
- Trained Astmatx personnel will be available to provide any additional technical support during the initial treatment sessions performed at a clinical site until the Investigator and his/her staff feel comfortable with the use of the device.

The proctor from Astmatx will evaluate the success of the training by observing and evaluating the proficiency of the Physician/Investigator in performing the bronchial thermoplasty procedure according to the Directions for Use (DFU).

- If necessary, additional training will be provided.

7.3 Detailed Study Description

An outline of the study design is presented as a Study Flow Chart in Figure 2.

The study procedures and assessments to be performed during the course of the study are described below and outlined in Table 2 and Figure 4.

7.3.1 Informed Consent

- Obtain a signed Informed Consent form from the subject prior to beginning the initial screening, including any necessary medication stabilization.
- Place the original signed Informed Consent form in the Subject Study Binder, and a copy of the signed Informed Consent form in the subject's medical record.
- Provide the subject with a copy of the signed Informed Consent for their records.
- The Informed Consent process (including the initial Informed Consent and any revised Informed Consent forms throughout the duration of the study) should be documented in the subject's study notes and appropriate CRF/eCRF.

7.3.2 Subject Identification Number

- Assign the subject a unique identification number (Subject ID number) at the time of signing the Informed Consent form.
- The subject ID number consists of the Site Number (assigned by the Sponsor, XXXXG), the Study Number (1002), the Subject Number (starting at 01 and increasing sequentially), and a 3 digit subject initials (AAA). For example, subject number 5 at site number XXXXG will be identified as “XXXXG-1002-05-AAA”.

[figure not shown]
Table 2: Study Procedures and Assessments

Procedure / Assessment	Screening/ Enrollment	1st Bronch.	F/U Visit 1	2nd Bronch.	F/U Visit 2	3rd Bronch.	6-wk F/U Visit T = 0	3-Monthly Safety Phone Calls	12-mo F/U Visit	3-Monthly Safety Phone Calls (Yr2 - 5)	Annual F/U Visits (Yr2 - 5)
Medical History	✓										
AQLQ (Juniper)	✓										
Spirometry ¹	✓	✓	✓	✓	✓	✓	✓		✓		✓
Physical Examination – to include SpO ₂	✓	✓	✓	✓	✓	✓	✓		✓		✓
Review of Asthma Symptoms, Exacerbations, Medications	✓		✓		✓		✓	✓	✓	✓	✓
Solicit Adverse Events	✓		✓		✓		✓	✓	✓	✓	✓
Solicit information on Emergency room visits for respiratory symptoms	✓		✓		✓		✓	✓	✓	✓	✓
Solicit information on hospitalizations for respiratory symptoms	✓		✓		✓		✓	✓	✓	✓	✓
Pregnancy Testing	✓	✓ ²		✓ ²		✓ ²					
Chest X-Ray – Lateral & PA	✓										
Blood Coagulation Panel (PT, PTT, INR) and Complete Blood Count (RBC, WBC, platelets)	✓										
Bronchoscopy for BT		✓		✓		✓					

¹ Perform pre-bronchodilator spirometry following a 12-hour abstinence from long-acting β_2 -agonist and a 4-hour abstinence from short-acting β_2 -agonists, and post-bronchodilator spirometry 15 minutes after the administration of 4 puffs (100 μ g per puff) of albuterol via a spacer.

² Perform pregnancy test prior to initiation of bronchoscopy if subject is a female of child-bearing potential

Figure 4: Chronology of Protocol Required Testing

